6.6.7.2. Other laboratory parameters

All other parameters collected on the eCRF will be listed in dedicated listings presenting all corresponding collected information on the eCRF.

- Coagulation: activated partial thromboplastin time (aPTT), prothrombin time (PT), international normalized ratio (INR), and PTT.
- Urinalysis: all urinalysis parameters
- HCV, HBV testing
- Hormone tests: TSH, free T4, ACTH
- ANCA, ANA, RF
- Pregnancy test

The listings of laboratory results will be provided for all laboratory parameters. The listings will be sorted by parameters and assessment dates or visits for each patient. Laboratory values that are outside the normal range will also be flagged in the data listings, along with corresponding normal ranges. A listing of CTCAE grading will also be generated for those laboratory tests.

In addition, listings of abnormal values will be provided for hematology, chemistry, urinalysis, coagulation parameters. If there is at least one abnormal assessment for any parameter, all the data for that laboratory parameter will be included into the listing.

For all tests not mentioned above but present in the clinical data, a listing of patients with at least one result for the relevant test will be provided.

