With respect to the potential immune-related AEs, 7 patients (14.9%) developed Grade 1-2 hypothyroidism, 3 patients (6.4%) Grade 1 hyperthyroidism, and 1 patient (2.1%) Grade 1 autoimmune hypothyroidism. In addition, diarrhea (27.7 %, all of Grade 1-2 severity), rash (17% all grades, 2.1% Grade 3), ALT increased (12.8% all grades, 4.3% Grade 3), and AST increased (8.5% all grades, 2.1% Grade 3) were reported. Both hyperthyroidism and hypothyroidism are expected AEs for both avelumab and axitinib. Rash, diarrhea and increased liver enzymes have also been reported with axitinib monotherapy. Medical review of these cases to confirm their immune-related nature is ongoing. In addition, there was one case of fatal myocarditis which was assessed as related to both avelumab and axitinib by the investigator and in which pathology confirmed an immune-mediated cause.

Seven (7) out of 47 treated patients included in the study database discontinued study treatment: 4 patients due to disease progression, 2 patients due to adverse event (fatal myocarditis and Grade 3 creatinine phosphokinase increased, 1 patient each), and 1 due to consent withdrawal.

In conclusion, as of 15 August 2016, the safety profile of the combination appears consistent with that of each study drug as monotherapy. Safety continues to be closely monitored by the B9991002 study team and discussed in regular teleconferences between the study team and the investigators.

In addition, as of 15 August 2016, 36 out of 47 patients in the clinical database were treated for at least 12 weeks prior to the analysis cut-off date and were included in the analysis of best overall response (BOR). The BOR included 1 patient with confirmed CR (2.8%), 15 patients with confirmed PR and 4 patients with unconfirmed PR (52.8%), 9 patients with SD (25.0%), 5 patients with PD (13.9%) and 2 patients not evaluable for response (5.6%; one patient died before the first oncologic assessment due to myocarditis, and another one who never started the combination treatment, discontinued axitinib treatment due to Grade 3 creatinine phosphokinase increased). The objective response rate (including confirmed and unconfirmed responses) is 55.6% (95% CI: 38.1-72.1).

Based on the safety and efficacy data described above, further investigation of avelumab in combination with axitinib in the patient population chosen for this study appears feasible.

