9.	Hematology, Blood Chemistry (full panel), and Coagulation: Required tests are listed in Table 7. Full chemistry panel (required tests are listed in Table 7) is required at screening, on Day 1 of each cycle. May also be performed when clinically indicated. Arm B (Sunitinib Arm): From Cycle 2 onward, Days 15 and 29 laboratory assessments will be performed by local laboratories unless the patient is visiting the site for other reasons. The patient will be instructed to email/fax the results of the laboratories assessments to the site and bring them in at the next visit. Arm A (this option is applicable only to patients on treatment with single agent axitinib, after they have visited the site every 2 weeks for additional 2 full cycles following avelumab permanent discontinuation): Days 15 and 29 laboratory assessments will be performed by local laboratories unless the patient is visiting the site for other reasons. The patient will be instructed to email/fax the results of the laboratories assessments to the site and bring them in at the next visit.
10.	Blood Chemistry (core panel): Core chemistry panel (required tests are listed in Table 7) is required on Days 15 and 29 of each cycle.
11.	Thyroid Function Tests: Free T4, TSH, tests will be performed at screening, Cycle 2 Day 1, Cycle 3 Day 1, then every 2 cycles thereafter. Additional tests should be performed when clinically indicated. Hypothyroidism should be treated per standard medical practice to maintain euthyroid state. See Table 7.
12.	ACTH: ACTH tests will be performed at screening, Cycle 3 Day 1, then every 2 cycles thereafter. Additional tests should be performed when clinically indicated. See Table 7.

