### **8.5. Abnormal Test Findings**

The criteria for determining whether an abnormal objective test finding should be reported as an AE are as follows:

- Test result is associated with accompanying symptoms; and/or
- Test result requires additional diagnostic testing or medical/surgical intervention; and/or
- Test result leads to a change in study dosing outside of protocol-stipulated dose adjustments or discontinuation from the study, significant additional concomitant drug treatment, or other therapy; and/or
- Test result is considered to be an AE by the investigator or sponsor.

Merely repeating an abnormal test, in the absence of any of the above conditions, does not constitute an AE. Any abnormal test result that is determined to be an error does not require reporting as an AE.

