### **Laboratory Abnormalities**

The laboratory results will be graded according to the NCI CTCAE v4.03 severity grade. The frequency of patients with laboratory test abnormalities will be summarized according to the worst grade for each laboratory test.

For laboratory tests without an NCI CTCAE grade definition, results will be categorized as normal (within normal ranges), abnormal, or not done.

Shift tables will be provided to examine the distribution of laboratory abnormalities.

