Albumin (hypoalbuminemia), Alkaline Phosphatase (alkaline phosphatase increased), Alanine Aminotransferase (ALT) (ALT increased), Amylase (serum amylase increased), Aspartate Aminotransferase (AST) (AST increased), Total Bilirubin (blood bilirubin increased), Cholesterol (cholesterol high), Creatinine (creatinine increased), Creatine Kinase (CPK increased), Potassium (hypokalemia/ hyperkalemia), Sodium (hyponatremia/ hypernatremia), Magnesium (hypomagnesemia/hypermagnesemia), Calcium (hypocalcemia/ hypercalcemia), Glucose (hypoglycemia/hyperglycemia), Gamma Glutamyl Transferase (GGT) (GGT increased), Lipase (lipase increased), Phosphates (hypophosphatemia), Triglycerides (hypertriglyceridemia).

Parameters with NCI-CTC grades not available:

Hematology and chemistry evaluations which cannot be graded per CTCAE criteria will be summarized as frequency (number and percentage) of patients with:

- shifts from baseline normal to at least one result above normal during on-treatment period
- shifts from baseline normal to at least one result below normal during on-treatment period

In this study, these apply to the following parameters:

- Hematology: Absolute Monocytes, Absolute Eosinophils, Absolute Basophils
- Serum Chemistry: Chloride, Total Urea, Uric Acid, Total Protein, C-Reactive Protein, Lactate Dehydrogenase (LDH), B-type natriuretic peptide (BNP), troponin, and CK-MB

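### TSH and free T4 go to listings only, so the SAP gives no by-arm laboratory shift summary for an expected toxicity of both avelumab and axitinib

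*SAP*

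**What the plan says.** Protocol 9.5, under Laboratory Abnormalities, makes two general statements: "For laboratory tests without an NCI CTCAE grade definition, results will be categorized as normal (within normal ranges), abnormal, or not done" and "Shift tables will be provided to examine the distribution of laboratory abnormalities". Neither names an exception.

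SAP 6.6.7.1 turns these into two tabulations. Parameters with a CTCAE grade get a baseline-by-worst-grade shift table. Parameters without one get counts of patients moving from a normal baseline to at least one value above normal, and to at least one below, during the on-treatment period. Each tabulation applies to an enumerated set of tests. The ungraded chemistry set is "Chloride, Total Urea, Uric Acid, Total Protein, C-Reactive Protein, Lactate Dehydrogenase (LDH), B-type natriuretic peptide (BNP), troponin, and CK-MB"; the ungraded hematology set is monocytes, eosinophils and basophils.

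SAP 6.6.7.2 deals with the remainder: "All other parameters collected on the eCRF will be listed in dedicated listings presenting all corresponding collected information on the eCRF". One entry in that group is "Hormone tests: TSH, free T4, ACTH".

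On the clinical side, the protocol's account of the Phase 1b safety data (Protocol Summary and Section 1.2.3) states: "Both hyperthyroidism and hypothyroidism are expected AEs for both avelumab and axitinib". Footnote 11 of the treatment-period Schedule of Activities sets the sampling for both arms: "Free T4, TSH, tests will be performed at screening, Cycle 2 Day 1, Cycle 3 Day 1, then every 2 cycles thereafter".

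**The concern.** A listing shows individual values, but it gives no count per arm and no denominator. For most of the tests in SAP 6.6.7.2 that matters little. TSH and free T4 differ because they monitor a toxicity expected from both experimental drugs, and they are measured repeatedly in every patient for that reason.

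Adverse event tables capture part of the same information, but through a filter. Under Protocol 8.5 an abnormal result becomes an adverse event only if it comes with symptoms, needs further work-up or intervention, changes dosing outside the protocol's rules or leads to significant added treatment, or is judged an event by the investigator or sponsor. The section adds: "Merely repeating an abnormal test, in the absence of any of the above conditions, does not constitute an AE". A patient whose TSH drifts out of range, who has no symptoms and who is only retested, can therefore appear in no table. The trial is open-label, so a laboratory count on the same planned schedule in both arms would be a useful check on events that depend on investigator judgement.

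Baseline status matters too. Exclusion criterion 10 lets in patients with hypo- or hyperthyroid disease that does not need immunosuppression. A shift counted from a normal baseline separates new abnormality from old; a flagged listing does not do so by arm.

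**Working it through.** The main check is a comparison of text; the SAP states no figure on this point to reproduce.

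**Where each test is tabulated**

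| Output in the SAP | Tests covered | TSH / free T4 included? |
|---|---|---|
| 6.6.7.1, graded summary and grade shift table | Enumerated hematology and chemistry tests | No |
| 6.6.7.1, ungraded shift counts | 3 hematology and 9 chemistry tests, including BNP, troponin and CK-MB | No |
| 6.6.7.2, listings | Coagulation, urinalysis, viral serology, hormone tests, autoantibodies, pregnancy | Yes, by name |
| 6.6.7.2, separate listing of abnormal values | Hematology, chemistry, urinalysis, coagulation | Not named |

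TSH and free T4 are in neither of the two summary lists, and no other SAP section tabulates them. That they have no CTCAE laboratory grade is inferred from their absence from the SAP's graded list.

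**Could a general sentence cover them?** SAP 6.6.7.1 opens by saying that results outside CTCAE are shown as below, within or above normal, and Protocol Table 7 puts the thyroid tests in its chemistry column. But that sentence sits in the section for hematology and chemistry parameters, the ungraded block then states which tests it applies to, and 6.6.7.2 assigns the thyroid tests elsewhere by name. A programmer following the SAP would produce listings only.

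**How much data is affected (illustration).** Inputs:
- Sampling at Cycle 2, Cycle 3, then every 2 cycles (Schedule of Activities, footnote 11).
- Cycle length 42 days, so Day 1 of cycle n falls on study day 42(n − 1) + 1.
- Planning median PFS of 11 months for sunitinib and 15.7 months for the combination in all comers (Protocol 9.1).
- 1 month = 30.4375 days (SAP 5.2.8).
- Assumption: treatment continues exactly to the planning median.

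Draw days: C2 = 43, C3 = 85, C5 = 169, C7 = 253, C9 = 337, C11 = 421, C13 = 505.

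- Arm B: 11 × 30.4375 = 334.8, about day 335. C2, C3, C5 and C7 are reached; C9 (day 337) is not. **4 draws.**
- Arm A: 15.7 × 30.4375 = 477.9, about day 478. C2, C3, C5, C7, C9 and C11 are reached; C13 (day 505) is not. **6 draws.**

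The Arm B count is at a margin: C9 falls two days after the assumed endpoint, inside the ±3-day visit window, so 5 would be equally defensible. The End of Treatment sample, and the Day 30 sample if taken within 30 days of last dose, come on top. Day 60 and Day 90 samples fall outside the on-treatment period of SAP 5.2.7 and would stay in listings in any case.

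**The case against.** The strongest reply has four parts.

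1. **The SAP is entitled to do this.** Protocol 9 and SAP 2 let the SAP change protocol plans, and only major changes to the primary endpoint or its analysis need an amendment. The SAP sends a whole class of tests to listings, which looks like a reporting convention rather than a thyroid oversight. Protocol 9.5 also states the normal/abnormal categories and the shift tables in separate sentences. This stands as far as it goes: it is a reporting gap and not a breach. But reading the two sentences together is natural, and the SAP does so for its other ungraded tests. It gives no reason for tabulating chloride and uric acid this way and not TSH.

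2. **Thyroid toxicity is already compared by arm.** TEAEs are shown by preferred term and worst grade (SAP 6.6.1.1), and irAEs with risk differences, confidence intervals and p-values (6.6.4). Any other preferred term reaching 10% in either arm becomes Tier-2 (3.5.1). The Phase 1b study recorded Grade 1-2 hypothyroidism in 7 of 47 patients (14.9%), so that threshold may well be met. The TEAE definition also separates new or worsening events from pre-existing ones. All this is correct for recorded events. It does not reach change that nobody records, and the irAE algorithm is narrower still, since Appendix 1 requires treatment to have been given before a case is selected, subject to medical review.

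3. **The residue is probably small.** Footnote 11 directs that hypothyroidism be treated, Table 6 starts endocrine treatment at Grade 1-2, and the Phase 1b data show low-grade thyroid change being recorded as adverse events. This is fair. It limits the importance of the point, but the size of the residue is unknown in either direction.

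4. **Draw counts are not a measure of harm.** Agreed. They describe how much data goes untabulated, and show neither bias nor a misjudged risk.

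**Conclusion.** The concern holds. For TSH and free T4 the SAP replaces the normal/abnormal summary and shift tables described in Protocol 9.5 with listings, without explanation, although thyroid dysfunction is an expected toxicity of both Arm A drugs and the SAP already applies the right summary to other monitored markers.

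The consequence is limited. No efficacy endpoint, error rate, power or patient monitoring is affected, and clinically recognised thyroid events remain tabulated by arm. What is missing is a by-arm count of new biochemical abnormality, chiefly asymptomatic, untreated change not judged an adverse event. The documents do not allow that count to be estimated. The figures of 4 and 6 scheduled draws are illustrative and rest on treatment ending at the planning median PFS; patients may stop earlier for toxicity or continue beyond progression. The change is worth making because it is cheap and closes a stated gap, but the gain is a modest one in safety reporting.

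**What to change.** Add TSH and free T4 to the list of parameters without CTCAE grades in SAP 6.6.7.1. For each test and arm, report the number and percentage of patients who move from a normal baseline to at least one on-treatment value above normal, and to at least one below. Use as denominator the patients with a normal baseline and at least one on-treatment value; the ungraded block states no denominator at present.

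Two additions are optional. ACTH has the same gap and could be added for consistency with Protocol 9.5. Combined TSH/free T4 categories, using the same-date rule that 6.6.7.1 applies to liver tests, would be more informative clinically, because Table 6 identifies secondary thyroid dysfunction by reading the two together.

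Arm A is expected to be sampled more often, which gives it more chances to show an abnormal value. The table should be read with exposure in mind, as should those for the other parameters in that block.

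The cost is two names in an existing list and one or two descriptive tables. No new data collection is needed.

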6.6.8. Vital signs

Weight for the purposes of dose calculation will be recorded at screening and within 3 days pre-dose Day 1 of each cycle. Height will be measured at screening only.

Vital sign summaries will include all vital sign assessments from the on-treatment period. All vital sign assessments will be listed, and those collected outside the on-treatment period will be flagged in the listing.

All vital sign parameters will be summarized using descriptive statistics (mean, SD, median, Q1, Q3, minimum, and maximum) of actual values and changes from baseline for each visit over time. End of Treatment visit will be summarized separately. The changes computed will be the differences from baseline.

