7.	Vital Signs: Vital signs to include, blood pressure, pulse rate. Vital signs will be monitored at screening and on Days 1, 15, and 29 of each cycle during the study. Blood pressure and pulse rate should be taken with the patient in the seated position after the patient has been sitting quietly for at least 5 minutes. Two blood pressure/pulse readings will be taken at least 1 hour apart at each clinic visit. Arm B (Sunitinib Arm): From Cycle 2 onward Days 15 and 29 vital signs will be performed and collected at home by the patient and communicated to the site study team during the telephone call (eg, nurse) in a standardized form, unless the patient is visiting the site for other reasons. Arm A (this option is applicable only to patients on treatment with single agent axitinib, after they have visited the site every 2 weeks for additional 2 full cycles following avelumab permanent discontinuation): Days 15 and 29 vital signs will be performed and collected at home by the patient and communicated to the site study team during the telephone call (eg, nurse) in a standardized form, unless the patient is visiting the site for other reasons.
8.	Home Blood Pressure Monitoring: All patients will receive home blood pressure monitoring devices and blood pressure will be monitored at home. Patients will monitor their blood pressure at least once daily (in Arm A before taking the morning dose of axitinib, and in Arm B before taking the daily dose of sunitinib during the 4 weeks of treatment and any time during the day in the 2 weeks off treatment), and blood pressure should be recorded in a patient diary. Patients should be instructed to contact the site immediately for guidance if their systolic blood pressure rises above 150 mm Hg, diastolic blood pressure rises above 100 mm Hg, or if they develop symptoms perceived to be related to elevated blood pressure (eg, headache, visual disturbances), although a different blood pressure threshold for contacting the site may be used according to the investigator's clinical judgment (see Section 5.4.6.3 ).

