3.2. Secondary Endpoints

3.2.1. Safety endpoints

- Adverse Events (AEs) as graded by National Cancer Institute (NCI) Common Terminology Criteria for Adverse Events (CTCAE) v4.03;

AEs will be graded by the investigator according to the CTCAE v4.03 and coded using the Medical Dictionary for Regulatory Activities (MedDRA);

- Laboratory abnormalities as graded by NCI CTCAE v4.03;
- Vital signs (blood pressure, pulse rate);
- Time to treatment discontinuation/failure due to toxicity;

Time to treatment discontinuation/failure due to toxicity is defined as the time from first dose of study treatment to discontinuation of study treatment (discontinuation of either avelumab or axitinib for arm A) due to an adverse event or death due to study treatment toxicity.

- Treatment discontinuation due to toxicity.

Treatment discontinuation due to toxicity is defined as the discontinuation of study treatment (discontinuation of either avelumab or axitinib for arm A) due to an adverse event or death due to study treatment toxicity.

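### From Cycle 2, Day 15 and Day 29 vital signs are mainly home readings in Arm B and mainly clinic readings in Arm A, and SAP 6.6.8 does not distinguish the setting

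*SAP*

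**What the plan says.** SAP 3.2.1 lists blood pressure and pulse rate among the secondary safety endpoints. SAP 6.6.8 sets the scope of their summary: "Vital sign summaries will include all vital sign assessments from the on-treatment period". The output is descriptive statistics of actual values and changes from baseline at each visit, and SAP 6.6 presents safety summaries by treatment arm. SAP 5.2.9 limits by-visit statistics to scheduled visits. SAP 3.4.1 takes the last assessment before treatment start as the safety baseline.

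Footnote 7 of the Protocol Schedule of Activities (screening and study treatment) sets the place of measurement. For the control arm: "Arm B (Sunitinib Arm): From Cycle 2 onward Days 15 and 29 vital signs will be performed and collected at home by the patient". The values are passed to the site by telephone, and the exception is "unless the patient is visiting the site for other reasons". For the experimental arm the option is narrower: "Arm A (this option is applicable only to patients on treatment with single agent axitinib, after they have visited the site every 2 weeks", for two additional full cycles after permanent avelumab discontinuation. For clinic visits the footnote requires: "Two blood pressure/pulse readings will be taken at least 1 hour apart at each clinic visit". It states no duplicate-reading rule for the home Day 15/29 values. Protocol 6.2 has the telephone data entered in the CRF, and says that after IA3 Day 15/29 safety assessments other than pregnancy tests are no longer required unless clinically indicated.

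**The concern.** Both arms contain a drug for which Protocol 5.4.6.3 sets out hypertension management, so a reader of the safety report will compare blood pressure over time between arms. From Cycle 2, the place and method of measurement at Day 15 and Day 29 depend largely on the assigned arm. Arm B's change from baseline at those visits is mostly a home value minus a clinic value. Arm A's is mostly a clinic value minus a clinic value. If home and clinic readings differ systematically, that difference appears in the by-visit table as if it were a difference between treatments. It also appears within Arm B as a step between Cycle 1 and Cycle 2. Nothing in SAP 6.6.8 or 5.2.9 would let the reader see this.

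**Working it through.** The plan gives no figure to reproduce. The check is a count of scheduled readings, a comparison of what each visit measures, and a bounded illustration.

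**Share of home readings.** Vital signs are scheduled on Days 1, 15 and 29 (footnote 7). In Cycle 1 all three are in clinic in both arms. From Cycle 2, Arm B has 2 of 3 (67%) under the home rule. Over c cycles the share is 2(c−1)/(3c) of all scheduled readings and (c−1)/c of Day 15/29 readings. For an illustrative c = 8 that gives 14/24 = 58% and 14/16 = 88%. These are upper limits, because a patient on site for another reason is measured there. In Arm A the share is 0 of 3 while avelumab continues. If avelumab is stopped permanently in Cycle 1, the two further full cycles are Cycles 2 and 3, so home readings start in Cycle 4 at the earliest.

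**What each visit compares** (baseline is a clinic value in both arms, since the home rule starts only at Cycle 2):

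| Visit | Arm A | Arm B | Arm B dosing phase |
|---|---|---|---|
| Cycle 1 Day 15 | clinic | clinic | within the 4-week dosing period |
| Cycle 1 Day 29 | clinic | clinic | nominally the day after the last dose of the cycle |
| Day 1, Cycle 2 on | clinic | clinic | after the 2-week off period |
| Day 15, Cycle 2 on | clinic, with the restricted exception | home, unless on site | within the dosing period |
| Day 29, Cycle 2 on | clinic, with the restricted exception | home, unless on site | nominally the day after the last dose of the cycle |

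Day 1 from Cycle 2 matches the arms on setting but not on exposure, because axitinib is continuous (Protocol 5.4.2). Protocol 1.2.2.3 gives half-lives of about 40 hours for sunitinib and 80 hours for its active metabolite. Over 14 days (336 hours), simple exponential decay leaves 2^(−336/40) = 2^(−8.4) ≈ 0.3% and 2^(−336/80) = 2^(−4.2) ≈ 5%. From Cycle 2, no routine visit matches the arms on both setting and exposure.

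**Possible size.** Let d be the home-minus-clinic difference, and pA and pB the shares of patients measured at home at a Day 15/29 visit. The method-only shift in the between-arm difference is d × (pB − pA). The values below are assumptions, not taken from the documents: |d| = 2 to 10 mm Hg, pB = 0.8 to 1.0, pA = 0 to 0.3.
- Smallest: 2 × (0.8 − 0.3) = 1 mm Hg.
- Largest: 10 × (1.0 − 0) = 10 mm Hg.
- At Day 1 visits: 0, since pA = pB = 0.

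If d is zero, the shift is zero at every visit.

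**The case against.** Much can be said for leaving the plan alone. The summaries are by visit, so Day 15/29 home values are not averaged with Day 1 clinic values. Home cuffs come from the sponsor (Protocol 5.4.6.3), and the seated, rested posture in footnote 7 is not expressly limited to the clinic. SAP 6.6.8 plans no between-arm contrast or test of blood pressure. Hypertension is also captured as a graded adverse event and, if it meets the Tier-2 frequency rule in SAP 3.5.1, receives a risk difference with a 95% CI (SAP 6.6.4). All of this stands, and it limits the consequence. It does not remove the gap. Setting still differs by arm at the affected visits, within-visit mixing can occur through the on-site exception, and change is still taken from a clinic baseline.

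A reader might infer several stronger points that the documents do not support:
- That home measurement is confined to Arm B. Footnote 7 extends it to a restricted Arm A group.
- That blood-pressure trends will differ because of method, or that the bias runs against Arm A. Neither the size nor the sign of d is given.
- That every on-sunitinib reading after Cycle 1 is a home reading. The on-site exception prevents this, and Day 29 nominally falls just after dosing ends.
- That the share of patients above the 150 mm Hg contact threshold would be distorted. SAP 6.6.8 plans no such proportion.

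**Conclusion.** The concern holds in a limited form. From Cycle 2, measurement setting is largely confounded with treatment arm at Day 15 and Day 29, and SAP 6.6.8 neither discloses nor examines this. Between-arm differences at those visits, and a step in Arm B after Cycle 1, could partly be a measurement artefact. The counts (up to 2 of 3 scheduled Arm B visits per cycle, none in Arm A on avelumab) follow from the schedule. The 1 to 10 mm Hg range rests entirely on assumed values and says nothing about direction. The effect is confined to descriptive summaries of a listed secondary safety endpoint before IA3. No hypothesis test, alpha allocation or sample size is touched. The change is worth making because the table as planned could mislead and the remedy is cheap.

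**What to change.** In SAP 6.6.8:
- Flag each vital-sign reading as clinic or home, from the telephone-call form or derived from the visit type. The documents do not show whether the CRF records the setting directly, so this needs confirming first.
- Show Day 15/29 home and clinic readings in separate rows or tables.
- Keep the planned summary and add a clinic-only by-visit summary as a sensitivity display. It should not replace the planned one, because Arm B's routine clinic readings after Cycle 1 fall at the end of the off period.
- In that display, point to Cycle 1 Day 15 (both arms in clinic and within the dosing period) and Cycle 1 Day 29 (both in clinic, nominally the day after the last sunitinib dose of the cycle). Label Arm B Day 1 readings from Cycle 2 as following the 2-week off period.

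The cost is SAP wording and one extra table, with fewer readings per visit in the clinic-only display. Study conduct does not change.
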